8.3. Tacrolimus (Prograf®)

AVAILABILITY

Tacrolimus is a commercially available macrolide compound with potent immunosuppressant properties. Tacrolimus is available for oral administration as capsules containing the equivalent of 0.5 mg, 1 mg, or 5 mg of anhydrous tacrolimus. For IV use, tacrolimus is available as a sterile solution in 1mL ampoules containing the equivalent of 5 mg of anhydrous tacrolimus per mL. The oral absorption of tacrolimus is erratic and incomplete; absolute bioavailability is approximately 25%; peak serum levels are seen 1 to 3 hours after an oral dose, and therapeutic trough blood concentrations have ranged from 5 to 20 ng/mL; tacrolimus is extensively metabolized in the liver, with only small amounts of unchanged drug (2% or less) being recovered in the urine; the elimination half-life of tacrolimus is approximately 10 hours. Tacrolimus suppresses both humoral (antibody) and cell-mediated immune responses. The compound is chemically distinct from cyclosporine but both agents elicit similar immunosuppressant effects. The immunosuppressive activity of tacrolimus is,

however, more marked than that of cyclosporine. Please refer to the agent's package insert for additional information.

PREPARATION FOR IV USE

Tacrolimus concentrate for injection must be diluted prior to IV infusion. For IV infusion, the concentrate is diluted with 0.9% sodium chloride or 5% dextrose injection to a concentration of 4-20 µg/mL. Preparation of the solution in polyethylene or glass containers allows storage for 24 hours beyond which unused solution should be discarded. A plasticized polyvinyl chloride (PVC) container should not be used because stability of the solution is decreased and polyoxyl 60 hydrogenated castor oil contained in the formulation may leach phthalates from PVC containers. Tacrolimus concentrate for injection and diluted solutions of the drug should be inspected visually for particulate matter and discoloration prior to administration whenever solution and container permit.

ADMINISTRATION

Tacrolimus is to be initiated on Day -2. Begin tapering between Day +90 to +120 in the absence of GVHD as tolerated with a goal of stopping by Day +150 to +180. See protocol text for tapering instructions, and for instructions for patients who are unable to take oral tracolimus.

STORAGE & STABILITY

Store tacrolimus capsules at controlled room temperature, 15-30°C (59-86°F) (Prod Info Prograf®, 1997). An extemporaneous suspension of tacrolimus with a final concentration of 0.5 milligrams/milli liter was stable for 56 days when it was stored at 24-26°C in glass or plastic amber prescription bottles.

TOXICITY

In patients receiving tacrolimus, 5% to 47% experienced anemia, 8% to 32% experienced leukocytosis, and 14% to 24% experienced thrombocytopenia. Rare cases of microangiopathic hemolytic anemia have been reported. Mild to moderate

hypertension was reported in 38% to 50% of patients receiving tacrolimus. Mild to moderate hypertension is a common adverse effect associated with tacrolimus therapy. Chest pain was reported in 19%. Antihypertensive therapy may be required. The most common adverse effects of tacrolimus have involved the central nervous system, and include headache (37% to 64%), tremors (48% to 56%), insomnia (32% to 64%), paresthesia (17% to 40%); and dizziness (19%). Tremor and headache may respond to a dosage reduction. Agitation, anxiety, confusion, seizures, depression, hallucinations, myoclonus, neuropathy, psychosis, incoordination, and abnormal dreams have been reported in 3% to 15% of tacrolimus-treated patients. Hyperkalemia (13% to 45%), hypokalemia (13% to 29%), hypophosphatemia (49%), and hypomagnesemia (16% to 48%) have been associated with tacrolimus therapy. In addition, hirsutism occurs only rarely with tacrolimus. Hyperuricemia has been reported in greater than 3% of tacrolimus-treated patients. Gastrointestinal adverse effects of tacrolimus have included nausea (32% to 46%), vomiting (14% to 29%), anorexia (7% to 34%), constipation (23% to 35%) and diarrhea (37% to 72%). Gingival hyperplasia observed in patients treated with cyclosporine has not been reported with tacrolimus therapy. Nephrotoxicity was reported in 36% to 40% and 52% of liver and kidney transplant patients receiving tacrolimus. Overt nephrotoxicity is usually seen early after transplantation and is characterized by an increased serum creatinine and a decrease in urine output. Hematuria has been reported in greater than 3% of tacrolimus-treated patients (Prod Info Prograf®, 1997). Abnormal liver function tests have been reported in 6% to 36% of patients receiving tacrolimus; ascites was reported in 7% to 27% of these patients. Other miscellaneous effects that have occurred in clinical trials include pain (24% to 63%), fever (19% to 48%), asthenia (11% to 52%), back pain (17% to 30%), and peripheral edema (12% to 36%). The incidence of hyperglycemia is 17% and may require therapy with insulin. Other less frequently occurring effects (greater than 3%) include abscess, chills, peritonitis, and photosensitivity reactions. Anaphylaxis has been reported in a few patients receiving intravenous tacrolimus. Tacrolimus contains castor oil which has been associated with anaphylaxis in other drugs containing castor oil derivatives. The incidence of bloodstream infection is 22%. Most infections are due to bacteria (81%), followed by

candidemia (14%), and cryptococcemia (5%). The source of bloodstream infection was primarily intravascular catheter, accounting for 39% of cases.

8.4. Methotrexate (Amethopterin®; MTX)

AVAILABILITY

Commercially available in 2mL, 4mL, 8mL, 10mL vials, or 1 g vials or preserved with benzyl alcohol. Please refer to the agent's package insert for additional information.

PREPARATION

The 1 gm vial may be diluted in 10 mL of saline or D5W.

COMPATIBILITY

Additive incompatibility: bleomycin, prednisone.

STORAGE & STABILITY

Stability and compatibility of methotrexate sodium solutions depend on several factors including the formulation of methotrexate sodium used, presence of preservatives, concentration of drug, specific diluents used, resulting pH, and temperature; the manufacturer's labeling and specialized references should be consulted for specific information. Methotrexate sodium solutions should be inspected visually for particulate matter and discoloration whenever solution or container permits.

ADMINISTRATION

Administer via slow IV push. Hydrate intravenously and induce diuresis.

TOXICITY

Hematologic including leukopenia (1.5%), thrombocytopenia (5%; nadir 5-12 days; recovery 15-27 days), anemia (nadir 6-13 days), pancytopenia (1.5%); gingivitis, glossitis, pharyngitis, stomatitis, enteritis; nausea/vomiting, anorexia, diarrhea;

hematemesis, melena; acute and chronic hepatotoxicity; transaminases increase 1-3 days after administration, hepatic fibrosis and cirrhosis with long-term therapy; pulmonary toxicity including pneumonitis, pulmonary fibrosis that is not dose dependent and may not be fully reversible; pruritis, urticaria, photosensitivity; CNS: drowsiness, blurred vision, tinnitus, malaise, seizures; nephropathy: cystitis, dysuria, azotemia, hematuria, renal failure; diabetes; when administered it may cause headache, back pain, rigidity.

DRUG INTERACTIONS

Aminoglycosides may cause decreased absorption of methotrexate, and increased renal toxicity. Folic acid may decrease response to methotrexate. The use of NSAIDs may increase methotrexate levels. Probenecid, salicylates, sulfonamides may increase therapeutic and toxic effect of methotrexate. Procarbazine can cause increased nephrotoxicity. Theophylline may increase plasma levels. Alcohol may result in increased hepatotoxicity. Thiazides may cause granulocytopenia. Food will delay absorption, and decreases methotrexate peak.

8.5. Antithymocyte Globulin (Rabbit) (Thymoglobulin®; rabbit ATG)

AVAILABILITY

Antithymocyte globulin is commercially available as a lyophilized powder for reconstitution containing 25 mg per vial. Each vial of powder is supplied with 5mL diluent.

STORAGE & STABILITY

Intact vials should be stored under refrigeration and protected from light. Do not freeze. Reconstituted solutions should be used within 4 hours. Further diluted solutions for infusion should be used immediately after dilution.

PREPARATION

Remove the ATG rabbit plus diluent from the refrigerator and allow them to reach room temperature prior to reconstitution. Reconstitute each 25 mg vial with 5mL of the diluent provided (sterile water for injection, USP). Rotate the vial gently to dissolve the powder. The resultant solution contains 5mg/mL of ATG rabbit. Withdraw the calculate dose and inject into D5W or NS for IV infusion. The final concentration should be 0.5 mg/mL. The solution should be administered through a 0.22 micron filter.

ADMINISTRATION

ATG rabbit will be administered IV at a dose of 2.0 mg/kg/day for 3 days (on Days -4, -3, and -2). The first dose should be infused over at least six hours, and subsequent doses over at least 4 hours. Infuse through a 0.22 micron in-line filter. Acetaminophen 650 mg PO, diphenhydramine 25-50 mg PO/IV, and methylprednisolone 1 mg/kg IV should be administered at the initiation and midway through each antithymocyte globulin (rabbit) infusion to minimize infusion reactions.

TOXICITY

Infusion reactions such as fever and chills are common, occurring in more than 10% of patient s. Steroids, antihistamines and acetaminophen will be given, as described above, to minimize infusion reactions. Hypersensitivity reactions, including anaphylaxis, occur less frequently and may also be minimized with steroids and antihistamines. Immunosuppression from antithymocyte globulin (rabbit) is associated with an increase in opportunistic infections, including fungal, viral, and pneumocystis infections.

8.6. Filgrastim (G-CSF: Granulocyte Colony-Stimulating Factor, Neupogen®)

AVAILABILITY

G -CSF is commercially available in 1.0 and 1.6mL vials containing 300 μ g and 480 μ g G-CSF, respectively. Please refer to the agent's package insert for additional information.

STORAGE & STABILITY

G-CSF is available as a sterile buffered protein solution and must be stored at 2-8°C. DO NOT ALLOW THE DRUG TO FREEZE.

ADMINISTRATION

Each vial should be entered only once, and the remainder of the vial discarded and not re-entered a second time. The daily dose should be injected subcutaneously in one or two sites. Standard dosing is 5 μ g/ kg daily as a subcutaneous injection. **TOXICITY**

Chills, nausea, anorexia, myalgias, bone pain, local injection site pain or inflammation, abnormal liver function tests, thinning of hair, and enlargement of the spleen. Rarely fluid retention and pericardial effusion. All of these are generally reversible when the drug is discontinued.

9. Statistical Considerations:

This is a multicenter phase II study of once daily intravenous Busulfex as part of reduced toxicity conditioning for patients with chemorefractory Hodgkin and non-Hodgkin lymphomas. The primary objective of this study is assess 1 year PFS of patients with refractory lymphomas undergoing allogeneic HSCT following conditioning with once daily Busulfex, fludarabine with or without thymoglobulin. Literature review suggests that for chemotherapy refractory relapsed Hodgkin and NHL patients 1 year PFS is below 15% (P0=0.15). We hypothesize that RIC transplantation should improve the 1 year PFS to this high risk group to 35% (P1=0.35). A sample size of 32 achieves 90% power to detect a

difference (P1-P0) of 0.2500 using a two-sided binomial test. The target significance level is 0.0500. The actual significance level achieved by this test is 0.0477. These results assume that the population proportion under the null hypothesis is 0.1000.

OS and progression free survival PFS will be estimated using the Kaplan-Meier method. OS is defined as the time from transplant to death, and surviving patients will be censored at last follow-up. PFS is defined as the time from transplantation to disease progression/relapse and/or death. OS and PFS data between subgroups will be analyzed by the log-rank test. NRM is defined as death from any cause other than disease progression or relapse. Cumulative incidences of NRM and relapse will be calculated with relapse or death as a competing event, respectively [37]. Comparisons between estimates of cumulative incidence will be made by using the Gray's test. The cumulative incidence of acute or chronic GVHD will be calculated with relapse or death without GVHD as competing events [37,38]. We anticipate that a maximum of 32 patients will be accrued to the study. Descriptive statistics (i.e. means, standard deviations, 95% confidence intervals for continuous variables, and frequencies for discrete data) will be computed for all correlative laboratory parameters. Given the small sample size in this phase II trial, a total of 32 patients limits our ability to perform inferential tests.

Accrual Estimate: 32 patients.

Accrual Period: Until 12/31/2013.

Safety/Stopping Rules:

Rates of non-relapse mortality and grade III-IV acute GVHD will be monitored on 6 monthly basis. The study will be halted for review by the data safety and toxicity committee (DSTC) if any of the following criteria are met.

1. Non-relapse mortality of >40% at day 100 after transplantation.
2. Cumulative incidence of grade III-IV acute GVHD is >40% at day 100 after transplantation.

Follow-Up Period : One year to evaluate progression free survival.

10. Records to be Kept:

Particular attention should be given to the specification of which data elements should be included in the Mary Babb Randolph Cancer Center Clinical Trials Research Unit OnCore database. The investigator will maintain adequate records in the Investigator Site File to enable the conduct of the study to be fully documented. All documents related to the conduct of the study will be kept on file in a readily accessible order. This file must be safely archived after the termination of the study.

Patient data collected on Case Report Forms (CRFs) should be sent to the Network Coordinator at the CTRU by fax at [contact] according to CRF submission guidelines provided by WVU. Data will be entered into the OnCore database.

Data Acquisition and Submission:

- Informed consent, including HIPAA authorization, must be obtained on all subjects prior to their participation.
- Always keep the original signed and dated consent form, sending a copy to the MBRCC CTRU with the source documents and eligibility checklist. A physician must sign the checklist confirming eligibility and intent to register the patient.
- In the event that the consent is signed, but later is either withdrawn or inactivated – even if the patient did not begin treatment – send a copy of the signed and dated consent to the MBRCC CTRU.
- Case report forms will be provided by MBRCC CTRU specific for this study.
- Submit original forms, done in black ink written legibly.
- Amended data should be identified as such, and the change(s) written (preferably) in red ink, initialed and dated.
- The source documentation for each subject should be clearly written/typed, dated and signed; all printouts, test reports, and procedures should be signed and dated.

- Baseline and on-study forms are due within 6 weeks of registration. Please use the date the consent was signed as the On-Study date.
- Source documents include, but are not limited to: medical records; chemotherapy treatment records/notes; radiation treatment records/notes; laboratory/pathology reports; radiology reports; EKGs, MUGA, etc. reports; correspondence related to patient care; home care documents.

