refractory disease was not significantly different from patients with chemosensitive disease. Various other investigators have retrospectively reported encouraging results with allogeneic HPCT in patients with relapsed and/or refractory Hodgkin's and NHL (13-18), none focusing primarily on refractory lymphomas.

A single institution study conducted at Ohio State University reported outcomes of allogeneic HPCT in patients with chemotherapy refractory aggressive NHL [19]. The study retrospectively analyzed outcomes of 46 patients with chemorefractory, aggressive NHL patients who had either stable disease (SD, n=32) or progressive disease (PD, n=14), respectively, following last salvage treatment. The median age was 46 years (range 22-63 yrs). 39 patients received matched sibling allografts, while 7 underwent unrelated donor transplantation. Diagnoses included diffuse large B-cell lymphoma (n=18), Burkitt's lymphoma (n=3), transformed B-cell lymphoma (n=5), mantle cell lymphoma (n=11) and peripheral T-cell lymphoma (n=9). The median number of prior therapies was 3 (range 2-8). Median follow-up of surviving patients is 5-years. 5-year overall survival (OS), progression free survival (PFS), and relapse rate for the whole cohort (n=46) were 38%, 34%, and 35% respectively. The rate of grade II-IV acute graft-versus-host disease (GVHD) was 43%. Of the 33 evaluable patients 75% developed chronic GVHD. Overall non-relapse mortality rate was 34%. The 5-year OS and PFS rates for patients with SD and PD were 46% vs. 21% (p-value=0.01; log-rank test), and 46% vs. 7% (p-value=0.0002; log-rank test) respectively. This study hints at potential of allogeneic transplant as curative therapy for a subset of chemorefractory patients with SD. These preliminary, encouraging results warrant confirmation in a well-designed clinical trial.

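### Rejecting the uncited 15% null in all 32 patients would not show a benefit specific to this regimen, nor necessarily any benefit in refractory patients

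*Combined protocol and SAP*

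**What the plan says.** Section 9 gives the benchmark as "Literature review suggests that for chemotherapy refractory relapsed Hodgkin and NHL patients 1 year PFS is below 15% (P0=0.15". The next sentence gives the alternative: "We hypothesize that RIC transplantation should improve the 1 year PFS to this high risk group to 35% (P1=0.35". No reference is attached to the 15%, and the treatment that produced it is not named. The power statement reads "A sample size of 32 achieves 90% power to detect a" and, on the next line, "difference (P1-P0) of 0.2500 using a two-sided binomial test". It adds "The target significance level is 0.0500" and "The actual significance level achieved by this test is 0.0477", and then says that the null proportion is 0.1000. The number of progression-free patients that counts as success is not stated.

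Section 1.2 says that patients refractory to salvage do poorly on conventional chemotherapy alone, without giving a rate. Section 1.3 describes a retrospective single-institution allograft series in chemorefractory aggressive NHL, whose five-year OS, PFS and relapse rate "for the whole cohort (n=46) were 38%, 34%, and 35% respectively". Of that series it says: "These preliminary, encouraging results warrant confirmation in a well-designed clinical trial".

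The primary objective (section 2.1) concerns chemotherapy-refractory lymphoma. Section 3.1 is wider. It also admits some chemosensitive relapses that are unsuitable for autografting, and some histologies regardless of response to chemotherapy. Section 9 pre-specifies no confidence interval for one-year PFS; its only 95% intervals are for correlative laboratory parameters.

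**The concern.** A single-arm test answers only the question that its null poses. Here the null appears to describe refractory patients who were not transplanted, while all trial patients are transplanted and some need not be refractory. Three things can therefore push the result above 15%: allografting in general, the busulfan-fludarabine regimen, and the inclusion of chemosensitive patients. The planned test cannot tell them apart.

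The title and section 1.6 centre on once-daily, exposure-targeted Busulfex, and the objective centres on refractory disease. Without a stated limit, a rejected null could be reported as evidence for either one, and the test by itself supports neither.

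**Working it through.** **Inputs.** From section 9: n = 32, P0 = 0.15 as stated, 0.10 as used in the power calculation, P1 = 0.35. From section 1.3: 34% five-year PFS in 46 allografted chemorefractory patients (stable disease, 32 patients, 46%; progressive disease, 14 patients, 7%), and, in a separate reduced-intensity series, a four-year current PFS of 55% in chemosensitive patients. X is the number of patients alive and progression-free at one year, taken as binomial.

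**1. The plan's own figure.** With null 0.10 and the two-sided region X = 0 or X ≥ 8:
- n = 32: alpha = 0.9^32 + P(X ≥ 8 | 0.10) = 0.0343 + 0.0117 = 0.0460; power at 0.35 = 91.8%.
- n = 31: alpha = 0.0382 + 0.0096 = 0.0477; power = 89.9%.

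The printed alpha matches n = 31 exactly, and n = 32 is close. Neither calculation uses the stated 15%.

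**2. Cut-offs that do test 15% with n = 32.**
- P(X ≥ 8 | 0.15) = 0.096, so X ≥ 8 is not a 5% test of 15%.
- X = 0 or X ≥ 9: 0.0055 + 0.0413 = 0.0468. Power at 0.35 is 84.2%.
- Equal tails (at most 0.025 each side), X = 0 or X ≥ 10: 0.0055 + 0.0156 = 0.0211. Power at 0.35 is 73.2%.

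**3. What the allograft series implies.** The subgroups average back to the total: (32 × 0.46 + 14 × 0.07)/46 = 34.1%. PFS cannot rise with time, so 34% at five years means at least 34% at one year in that series. The trial's one-year target is 35%.

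**4. Chance of rejecting 15%, P(X ≥ c | p), n = 32.**

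| True one-year PFS | X ≥ 9 | X ≥ 10 |
|---|---|---|
| 34% | 81% | 69% |
| 25% | 41% | 26% |

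A regimen giving only the 34% seen in that series would reject 15% in most trials. One giving 25% would do so in roughly a quarter to two fifths of them.

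**5. Effect of chemosensitive patients.** Suppose m of the 32 are chemosensitive with 55% PFS and the other 32 − m have exactly the null 15%, so there is no benefit in refractory patients. The count m is an assumption, and 55% is a four-year figure borrowed for illustration. X is then Bin(m, 0.55) + Bin(32 − m, 0.15).

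| m | Overall PFS | X ≥ 9 | X ≥ 10 |
|---|---|---|---|
| 4 | (2.2 + 4.2)/32 = 20% | 16% | 8% |
| 8 | (4.4 + 3.6)/32 = 25% | 40% | 25% |
| 12 | (6.6 + 3.0)/32 = 30% | 68% | 51% |

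**The case against.** The strongest reply is that nothing in the protocol is contradictory. A reader might infer that the 34% series refutes the 15% null. It does not: 15% without a transplant and 34% after one can both be true. Section 9 credits the expected gain to transplantation, and section 1.2 supplies the contrast with conventional chemotherapy. This stands. What remains is that the benchmark has no citation and no named treatment.

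Second, the protocol plans no PFS comparison with another conditioning regimen, its objective is to assess one-year PFS, and section 9 itself says that 32 patients limit inference. This also stands. A reader might go further and conclude that a positive result would show nothing. That is too strong: it could support the transplant strategy against its benchmark.

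Third, 34% does not represent allografting as a whole. It is one retrospective series of 46 aggressive NHL patients with no Hodgkin diagnosis listed, and it splits into 46% and 7% by disease status. Taking 34% as 16/46 (an assumption), the exact 95% interval is 21% to 50%. Section 1.3 also reports a poor outcome, without a rate, for chemorefractory patients in the reduced-intensity series, and 21% three-year PFS for transformed disease in a third series. This stands, and it rules out a tempting remedy, namely a claim of improvement whenever the lower limit exceeds 34%. That rule would set a one-year limit against a five-year estimate and treat that estimate as fixed.

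What the reply leaves untouched is the gap between the refractory population named in the objective and null and the wider population in section 3.1.

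**Conclusion.** The point holds as a limit on interpretation. Rejecting 15% in all 32 patients does not show a benefit specific to busulfan-fludarabine, nor necessarily a benefit in refractory patients. A true 34% would reject 81% or 69% of the time, and a true 25% would reject 41% or 26%. With no benefit at all in refractory patients and 8 of 32 chemosensitive at 55%, the test would still reject 25% to 40% of the time.

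This rests on reading the 15% as a non-transplant rate, which the text suggests but does not state, and on the assumed case mix. The result in step 3 of the working, at least 34% at one year, applies to that series only.

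A reader who takes the cut-off X ≥ 8 from the power statement would get 90% and 57% for true rates of 34% and 25%. Those figures belong to the 0.10 null and should not be used for 15%.

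The mismatch between 0.15 and 0.10 is a separate error. At 15% versus 35%, 32 patients give about 73% to 84% power, not 90%.

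**What to change.** In section 9:
- Cite the source of the 15% and name the treatment and population behind it.
- State that rejection supports the transplant strategy against that benchmark, within the limits of a single-arm study, and not this regimen over other allografts.
- Pre-specify one-year PFS with an exact 95% interval, overall and in patients chemorefractory at transplant. Use the protocol's own definition of refractory (no complete or partial remission), and say how untreated relapses are classed. Base any statement about refractory patients on the second interval.
- State the rejection rule. The exact equal-tailed interval excludes 15% from 10 of 32 upward, because P(X ≥ 9 | 0.15) = 0.041 exceeds 0.025 and P(X ≥ 10 | 0.15) = 0.016 does not.
- Cite the 34% series only as context, with its five-year time point and case mix. Set no rule that the lower limit must exceed 34%.
- Separately, reconcile the 0.15 and 0.10 nulls and restate the power.

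The interpretive changes need no extra patients. They cost a narrower claim and one extra, wider interval. For illustration, 11/32 gives 18.6% to 53.2% and 8/24 gives 15.6% to 55.3%, a width of about 40 points instead of 35. Correcting the null means either accepting the lower power at 32 patients or revisiting the sample size.

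### Section 9 labels the null as P0=0.15 but computes 32 patients and 90% power for a null of 0.10; at 0.15, exact power is at most 84.2%

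*Combined protocol and SAP*

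**What the plan says.** All the relevant figures stand in Section 9, Statistical Considerations.

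- The benchmark: "Literature review suggests that for chemotherapy refractory relapsed Hodgkin and NHL patients 1 year PFS is below 15% (P0=0.15").
- The target: "We hypothesize that RIC transplantation should improve the 1 year PFS to this high risk group to 35% (P1=0.35").
- The sample size: "A sample size of 32 achieves 90% power to detect a" "difference (P1-P0) of 0.2500 using a two-sided binomial test". The target significance level is 0.05.
- The size of the test: "The actual significance level achieved by this test is 0.0477".
- The null behind these results: "These results assume that the population proportion under the null hypothesis is 0.1000".

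The section gives no rejection cut-off. Accrual is capped at the same number: "We anticipate that a maximum of 32 patients will be accrued to the study". OS and PFS are to be estimated by Kaplan-Meier. After a sentence on the correlative laboratory parameters, the section adds: "Given the small sample size in this phase II trial, a total of 32 patients limits our ability to perform inferential tests".

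**The concern.** The paragraph contradicts its own symbols. With P0=0.15 and P1=0.35, P1−P0 is 0.20, yet it prints 0.2500, which requires a null of 0.10. A reader who takes P0 at face value will believe that the trial has 90% power to distinguish 35% from 15%.

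Two things are at stake. First, this is the only power justification for the primary endpoint, and it does not apply to the null it is labelled with. Second, with two nulls in print and no cut-off, some results can be called a success against one benchmark and a failure against the other. The choice between them could then be made after the data are seen.

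**Working it through.** **Inputs, all from Section 9:** n = 32; P1 = 0.35; two-sided binomial test; target size 0.05; printed size 0.0477; printed power 90%; null either 0.15 (label) or 0.10 (calculation).

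**Formula.** With X the number alive and progression-free at 1 year, P(X ≥ c | p) = Σ C(32, x) pˣ (1−p)³²⁻ˣ over x = c to 32. Size is the probability of the rejection region at the null; power is its probability at 0.35.

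**1. The plan's own figure, null 0.10.**
- P(X=0) = 0.0343 and P(X≥8) = 0.0117.
- The region {0 or ≥8} has size 0.0343 + 0.0117 = 0.0460 and power 0.918.
- At n = 31 the same region has size 0.0382 + 0.0096 ≈ 0.0477 after rounding, and power 0.899.

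The printed 90% is therefore recovered at null 0.10. The printed size of 0.0477 matches 31 patients rather than 32. That is a side observation: the region is inferred, because the plan prints none.

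**2. The labelled null, 0.15, n = 32.**

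| Upper cut-off | Upper tail at 0.15 | Power at 0.35 |
|---|---|---|
| ≥8 | 0.0958 | 0.918 |
| ≥9 | 0.0413 | 0.842 |
| ≥10 | 0.0156 | 0.732 |
| ≥11 | 0.0052 | 0.595 |

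Lower tail at 0.15: P(X=0) = 0.0055 and P(X≤1) = 0.0366. The admissible two-sided regions are:
- {0 or ≥9}: 0.0055 + 0.0413 = 0.0468, power 84.2%.
- {0 or ≥10}, at most 2.5% in each tail: 0.0055 + 0.0156 = 0.0211, power 73.2%.
- {≤1 or ≥11}, filling the lower tail first: 0.0366 + 0.0052 = 0.0419 before rounding of the parts, power 59.5%.

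**3. Why 84.2% is a ceiling.** At 0.15 the single-outcome probabilities for X = 2 to 8 are 0.0852, 0.1503, 0.1923, 0.1900, 0.1509, 0.0989 and 0.0545. Each exceeds 0.05 alone, so none can belong to a non-randomised region of size 0.05 or less. Only 0, 1 and 9 or more remain. Outcomes 0 and 1 add almost nothing to power at 0.35 (together 0.00002), so the maximum is P(X≥9 | 0.35) = 0.842. The shortfall from the printed figure is at least 90 − 84.2 = 5.8 points, and 90 − 73.2 = 16.8 points with 2.5% per tail.

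**4. Like-for-like comparison at 0.35, n = 32.**

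| Rule | Null 0.10 | Null 0.15 |
|---|---|---|
| Maximum over all regions | 96.4% (≥7, size 0.0358) | 84.2% |
| At most 2.5% per tail | 91.8% (≥8) | 73.2% (≥10) |
| Lower tail first | 91.8% (0 or ≥8) | 59.5% (≤1 or ≥11) |

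A normal approximation does not restore 90% at null 0.15: it gives 87.3% one-sided and 81.7% two-sided.

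**5. Effect on reading a result.** For 8 of 32 (25%) the upper tail is 0.0117 at 0.10 and 0.0958 at 0.15. The exact 95% confidence interval is 11.5% to 43.4%, so its lower limit falls between the two nulls. If true 1-year PFS is 0.35, exactly 8 successes occurs with probability 7.7%.

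**The case against.** The strongest reply is that the power statement discloses its own null. Read on those terms it is nearly right, 91.8% against a printed 90%, and a literature rate described as under 15% does not exclude 10%. This part stands: the documents do not settle which null was meant. It does not remove the contradiction, because P0 is explicitly set to 0.15, P1−P0 is then not 0.25, and no literature basis is given for 0.10.

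A second reply is that little depends on the test. Section 9 plans Kaplan-Meier estimation, sets no efficacy success rule, and warns that 32 patients limit inferential testing (possibly only for the laboratory parameters). The stopping rules use non-relapse mortality and acute GVHD, not PFS. This also stands, and it confines the harm to the stated power and the interpretation of the result; trial conduct is unaffected. Even so, the section names a test with a size and a power, and such a test needs one null.

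Finally, comparing 91.8% with 84.2% mixes rejection rules. That is fair, and the matched comparison in the working shows larger gaps. The 84.2% ceiling is the figure most favourable to the plan.

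**Conclusion.** The concern holds. The 90% power attached to 32 patients applies to 0.10 versus 0.35. For the labelled comparison of 0.15 versus 0.35, exact power is at most 84.2%, and 73.2% with 2.5% per tail. In terms of type II error, that is at least 16%, or 27% with 2.5% per tail, against the stated 10%.

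These figures assume that all 32 patients have known 1-year status and that the test is exact and non-randomised with total size no more than 0.05. The conclusion does not depend on which null the sponsor intended, because the paragraph needs correcting either way. It should be fixed before the primary result is interpreted, since it affects the only power statement for the primary endpoint.

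**What to change.** Use one null throughout Section 9, and state its justification, cut-off, actual size and power. State that only the upper cut-off counts as evidence of benefit; 0 of 32 would reject in the direction of worse PFS.

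- **If 0.15 is kept:** delete 0.2500, 0.1000 and 0.0477, and replace 90% with the power of the chosen region. Examples: reject at 0 or at 9 or more of 32, size 0.047, power 84% at 0.35; or reject at 0 or at 10 or more, size 0.021, power 73%.
- **If 0.10 was intended:** change P0 to 0.10 and give its literature basis. Example: reject at 0 or at 8 or more of 32, size 0.046, power 92% at 0.35.

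The null and the split of alpha are the sponsor's choice. The document is dated 11 October 2013 and accrual runs to 31 December 2013, so outcome data may already exist. The choice should be made without reference to them, and its date and reason recorded.

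The cost is one reworded paragraph. No extra patients are needed if the lower power at 0.15 is accepted. Holding 90% exact power at 0.15 would first be possible at 38 patients (one-sided 0.05) or 48 (2.5% per tail).
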